### Inclusion Criteria

- Age = 18 or older
- At least 6 months post-stroke
- Moderate upper limb impairment with the ability to participate in hand task practices
- Fingertip touch sensory deficits (e.g., Monofilament>2.83, 2-point discrimination>5mm, sense of numbness, tingling)

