### Exclusion Criteria

- Complete upper limb deafferentation
- Rigidity (Modified Ashworth Scale=5)
- Botulinum toxin injection within 3 months prior to enrollment or during enrollment
- Brainstem stroke
- Comorbidity (peripheral neuropathy, orthopaedic conditions in the hand that limit ranges of motion, premorbid neurologic conditions, compromised skin integrity of the hand/wrist due to long-term use of blood thinners)
- Concurrent upper extremity rehabilitation therapy
- Language barrier or cognitive impairment that precludes following instructions or providing consent
- MRI incompatible.
- Screening: Eligibility will be determined based on the potential participant's verbal disclosure.
- Inclusion of Women and Minorities: We will include chronic stroke survivors of all genders and all racial and/or ethnic groups that are representative of the demographics of Americans who had a stroke. We will not exclude people based on sex/gender, racial or ethnic group. Specifically, according to data from the 2013 Behavioral Risk Factor Surveillance System, BRFSS (CDC), 2.7% of men and 2.7% of women  $\geq$  18 years of age had a history of stroke. Thus, approximately the same number of women and men will be recruited for this study. Also, according to the same data, 2.5% of non-Hispanic whites, 4.0% of non-Hispanic blacks, 1.3% of Asian/Pacific Islanders, 2.3% of Hispanics of any race, 4.6% of American Indian/Alaska Natives, and 4.6% of other races or multiracial people had a history of stroke. Thus, considering the stroke prevalence in each racial and ethnic group from the BRFSS together with the racial and

ethnic distribution of the American population from the 2010 U.S. Census, we will target enrollment of stroke survivors of all racial and ethnic groups accordingly.

- Exclusion of Children: We will recruit individuals who have had a stroke at least 6 months ago, who are 18 years old or older. Children under the age of 18 years will be excluded. The rationale for exclusion of children is that stroke predominantly occurs in adults, and stroke is very rare in children.

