For the MRI, all participant receiving MRI are required to complete a screening questionnaire to ensure that the person does not have any loose metal objects such as earrings or nose rings or a piece of metal in the body such as a fragment in the eye, aneurysm clips, ear implants, spinal nerve stimulators, a pacemaker, or an implant electrical device. Persons with potential for pregnancy will be excluded. Each person

will be screened before each MRI assessment. To prevent hearing loss, the participant will be asked to wear earplugs and headphones for MRI.

Potential risks that may be associated with use of wrist vibration (wrist skin irritation, increased upper limb pain, increased spasticity, weakened grip strength, worsening of hand sensation, and worsening of hand dexterity) will be systematically assessed at all times (for evaluation time points including after each week of continuous therapy and 1-month follow-up, as compared to baseline) as safety data. Negative changes in these safety measures will be communicated to the participant immediately and be explained. In addition, any other adverse events regardless of whether it is related to the device or not will be explicitly asked and recorded at all evaluation time points as well as any time they occur. All of these safety data and adverse event information, in addition to the daily safety screening and fatigue/pain monitoring data, will be reported to the DSMB, IRB, clinicaltrials.gov, and in publications.

Participants will be notified if we learn anything that might make them change their mind about participating in the study. Participants will be informed that they can drop out of the study at any time without penalty.

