Function, Box and Block, and Action Research Arm scores) are assessed after each week of therapy and at 1-month follow-up, compared to baseline. In addition to the hand function scores, broad aspects of safety will be systematically assessed at all evaluation time points for all participants as part of clinical assessments. These safety data will include any wrist skin irritation (verbal report and/or visual examination), increased upper limb pain level (on a visual analog pain rating scale from 1 to 10), increased spasticity (on the Modified Ashworth Scale), weakened grip strength (using Jamar grip dynamometer), and worsening of hand sensation (using the Semmes-Weinstein Monofilament Test score), compared to baseline. Decline will be considered as an adverse event if a reasonable criterion is met: if the participant exhibits wrist skin irritation that did not exist prior to the intervention, if the pain level increases by more than 2 points, if the Modified Ashworth Scale increases by more than 1 level (equivalent to the effect size of botulinum toxin A), if grip strength declines by more than 20% from the baseline which is approximately 2 standard deviation of the population data, if the Monofilament Test declines by one category (e.g. “normal” to “diminished light touch”) with a change of more than two points, and/or if the hand function scores decline by more than the larger of the minimum detectable change and the minimal clinically meaningful difference reported in literature. Negative changes in these measures will be communicated to the participant immediately and be explained. A potential need for medical attention will be discussed.

Any adverse events, regardless of whether it is related to the device or not, will also be explicitly asked and recorded at all evaluation time points. These safety assessments will add additional 10 minutes to the clinical assessment at each evaluation time point.

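### From a baseline of Ashworth 4, or of pain 8 or more, the spasticity or pain adverse-event criterion cannot be met by that measure alone

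*Combined protocol and SAP*

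**What the plan says.** Section 12.0 compares several safety measures with baseline at each evaluation and then says when a worsening counts: "Decline will be considered as an adverse event if a reasonable criterion is met". For spasticity the condition is "if the Modified Ashworth Scale increases by more than 1 level (equivalent to the effect size of botulinum toxin A". For pain the instrument is described as "increased upper limb pain level (on a visual analog pain rating scale from 1 to 10", and the condition is "if the pain level increases by more than 2 points". The list also covers new wrist skin irritation, loss of grip strength, worse monofilament results and decline in hand function. The items are joined so that any one is enough.

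On entry, the Exclusion Criteria in Section 5.0 remove "Rigidity (Modified Ashworth Scale=5". The Inclusion Criteria limit impairment only in words: "Moderate upper limb impairment with the ability to participate in hand task practices". No number caps the Ashworth score below 5, and nothing caps baseline pain.

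Adverse-event status has consequences in Section 12.0. The DSMB otherwise meets at the end of the study, but the investigator must tell it at once when an adverse event occurs. The IRB also receives adverse events as they arise. For worsening of any size the same section says: "Negative changes in these measures will be communicated to the participant immediately and be explained". Safety data are tabulated at each time point. Section 10.0 adds that "any other adverse events regardless of whether it is related to the device or not will be explicitly asked and recorded".

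**The concern.** A threshold for change from baseline, applied to a bounded scale, cannot be met by someone who starts too close to the top. The protocol has two such thresholds and no clause for high baselines. For spasticity the gap also touches eligibility: a person can enter at the level just below rigidity, move to rigidity during treatment, and not meet the criterion meant to detect worsening spasticity.

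Increased pain and increased spasticity are both named in Sections 10.0 and 14.0 as potential risks of wrist vibration. Participants who enter with the most spasticity or pain are those for whom the criterion on that measure cannot operate. At stake is prompt oversight. Without adverse-event status, the change reaches the DSMB with the rest of the data at the end of the study, and nothing written requires it to be reported to the IRB when it happens.

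**Working it through.** The plan gives no figure to reproduce here; the check is scale arithmetic.

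**Inputs**
- Spasticity threshold: a rise strictly above 1 level (Section 12.0).
- Ashworth score excluded at entry: 5 (Exclusion Criteria).
- Pain scale 1 to 10, threshold a rise strictly above 2 points (Section 12.0).
- Assumptions: Ashworth 4 and 5 are adjacent levels, and 5 is the top. The documents label 5 as rigidity but do not state the range or the steps.

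**Formula.** For baseline *b*, scale maximum *M* and threshold *t*, the largest possible rise is *M* − *b*. The criterion can be met only if *M* − *b* > *t*.

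**Ashworth, *M* = 5, *t* = 1**

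| Baseline | Largest rise | Can exceed 1? |
|---|---|---|
| 1 | 5 − 1 = 4 | yes |
| 2 | 5 − 2 = 3 | yes |
| 3 | 5 − 3 = 2 | yes, only by reaching 5 |
| 4 | 5 − 4 = 1 | no |

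If the coding starts at 0, that baseline also passes (5 − 0 = 5). Only baseline 4 fails. The statement that a change from 4 to 5 does not meet the criterion does not need the assumption that 5 is the top; the statement that nothing from baseline 4 can meet it does. Two participants can also end in the same state with different results: 3 to 5 is a rise of 2 and counts, while 4 to 5 is a rise of 1 and does not.

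**Pain, *M* = 10, *t* = 2**

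| Baseline | Largest rise | Can exceed 2? |
|---|---|---|
| 7 | 10 − 7 = 3 | yes |
| 8 | 10 − 8 = 2 | no |
| 9 | 10 − 9 = 1 | no |
| 10 | 10 − 10 = 0 | no |

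In general 10 − *b* > 2 requires *b* < 8, so the result is the same whether the scale is scored in whole numbers or continuously.

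**Sensitivity to wording.** If the thresholds were read as at least 1 level and at least 2 points, 4 to 5 would count and only pain baselines above 8 would be blocked. The text is strict for both measures, so this reading is not available as written.

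**How many people.** The documents give no baseline distribution, so the number affected cannot be estimated and may be zero. One affected participant would be 1/8 = 12.5% of those recruited (Section 6.0), or 1/4 = 25% of the number targeted to complete data collection (Section 11.0).

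**The case against.** The strongest reply is that failing one criterion is not the same as going unnoticed. A hand that becomes rigid may also lose more than 20% of grip strength or decline in hand function, and either can make the change an adverse event. Adverse events are also asked about openly, outside the numeric list. Pain is rated before and after every session, compared with baseline and used to adjust tasks; pain that cannot be managed ends participation, and the DSMB reviews discontinuations. The DSMB sees individual data, includes a stroke neurologist who directs a spasticity clinic, and reviews the safety plan before enrolment.

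All of this stands as a limit on the point. A reader might infer that worsening to rigidity is simply not an adverse event, or that nobody would see it. The documents do not support that; they show only that the spasticity criterion is not met by that change. The other routes do not close the gap, though. They depend on a second measure also worsening or on someone's judgement, whereas the protocol gives spasticity and pain their own numeric rules.

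Two further objections are fair. Not being excluded by number is not the same as being eligible: a person at Ashworth 4 must still have moderate impairment and be able to practise hand tasks, which may leave nobody at that level. And an entry exclusion is not a harm threshold. A reader might infer that reaching Ashworth 5 must count as an adverse event because it is excluded at entry, but the Exclusion Criteria do not say so. That is for the sponsor and DSMB to decide.

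Nothing should be drawn from the botulinum toxin comparison, because the documents do not give the size of that effect.

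**Conclusion.** The point holds in a limited form. As written, the spasticity criterion is not met by a change from Ashworth 4 to 5 and, taking 5 as the top of the scale, cannot be met from baseline 4. The pain criterion cannot be met from a baseline of 8 or more. What is lost is automatic classification on that measure, and so the guaranteed immediate notice to the DSMB and as-it-occurs reporting to the IRB. Communication to the participant, tabulation, open adverse-event capture and the other criteria remain. Because the study is small and requires moderate impairment, the practical effect is probably small and may be nil. It still merits correction, since it concerns two named device risks and is cheap to repair.

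**What to change.** Reconcile the Exclusion Criteria in Section 5.0 with the adverse-event criteria in Section 12.0 so that each criterion can be met from every eligible baseline. Add a ceiling clause for the Ashworth and pain measures that says what counts when the baseline leaves too little room for the stated rise. The sponsor and DSMB should set the trigger, and should state whether reaching the level excluded as rigidity is itself an adverse event. The trigger needs a defined size, so that trivial movement on a visual analog scale is not reported. State the Ashworth coding and its top level once, and use them in both sections.

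This needs a clause in Section 12.0 and one line on coding, with no new measurement. The downside is possibly a few extra adverse-event reports from participants with high baseline spasticity or pain. The DSMB's review of the safety plan before enrolment is the natural time to settle it.

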## 13.0 Withdrawal of Subjects (if applicable)

- Subjects who do not show up on scheduled visits may be withdrawn by the investigator.

- For those who voluntarily withdraw from the research, their data collected up to that point may be used by the investigator.

## 14.0 Risks to Subjects

- There is a slight risk for loss of confidentiality although researchers will take appropriate steps to protect any information collected about the participants. There is a minor risk of physical and mental fatigue from engaging in the study activity. There is a minor risk of skin irritation from wearing the wristband. There is a minor risk of discomfort in moving the arm/hand while wearing a device on the wrist, although the TheraBracelet device weighs only 40 g.
- For the EEG assessment, there is a minor risk of discomfort in wearing a head cap attached with a bundle of wires. Also, the gel used for the electrodes will get hair messy. For the MRI, there is a serious risk that MRI could move iron-containing objects in the MRI room, which could in the process possibly harm the person. The 3T MRI scanner is unsafe for pregnancy. There is discomfort by claustrophobia and by the loud banging noise. Temporary hearing loss has been reported from the loud noise from the MRI machine. The person may also feel uncomfortable as s/he will be asked not to swallow for a while.
- Potential risks that might be associated with use of wrist vibration for a prolonged time include wrist skin irritation, increased upper limb pain, increased spasticity, weakness, and worsening of hand sensation or dexterity. These risks are expected to be rare because the intensity of vibration used in TheraBracelet is subliminal while we are exposed to higher-intensity, suprathreshold vibration daily (e.g. from a phone, car). Currently there is no vibration exposure guideline for this small level of vibration, as the U.S. Occupational Safety and Health Administration provides vibration exposure guidelines only for high-intensity vibration such as jackhammers and hand-held powered drills. Currently there are no known side effects using this small imperceptible (unfelt) level of vibration used in the proposed study. TheraBracelet has been used during hand task practice therapy in chronic stroke survivors for a total of 12 hours without any adverse events including no skin irritation in our pilot study. In addition, the investigators have used TheraBracelet vibration for 12 hours/day every day for 1 month continuously with no safety issues, including no skin irritation. Nonetheless, safety of using TheraBracelet will be systematically monitored.

## 15.0 Potential Benefits to Subjects and Others

- There may be no benefit from participating in this study. The potential benefit is that the vibration the participant receives may help recover their hand function, although this cannot be guaranteed. Another potential benefit is that the hand therapy the participant receives may help recover their hand function, although this cannot be guaranteed. The knowledge regarding the potential of using unperceivable vibration as a therapy booster is important to improve hand function and activities of daily living for people who had a stroke and may benefit stroke survivors in general. The risks are deemed reasonable in relation to the potential gain of knowledge regarding this technology's efficacy in enhancing recovery of hand function after stroke.

## 16.0 Sharing of Results

- If the subject agrees, the data collected and generated from this study will be shared to the Registry for Stroke Recovery (RESTORE-Pro#00037803) by the subject's registry ID. Sharing data from this study with the registry will allow for more targeted recruitment efforts in the future and allow researchers at MUSC to have a more complete registry with key stroke recovery elements including common data and physical function characteristics that are applicable to multiple studies. MUSC researchers and collaborating facilities will be able to query data sets to learn more about recovery of subjects after their stroke through institutionally managed secure servers that will assure HIPAA privacy and security compliance.

## 17.0 Drugs or Devices

- The vibrators and watches will be stored in the laboratory and will be provided to the participants by the study personnel.

